### Secondary Endpoints(s):

- To assess the renal safety of Stribild® or Genvoya® or unbranded elvitegravir/cobicistat/emtricitabine/tenofovir alafenamide PEP
- To document the side effect profiles of Stribild® or Genvoya® or unbranded elvitegravir/cobicistat/emtricitabine/tenofovir alafenamide given as PEP to HIV-1 seronegative adults
- To assess adherence to Stribild® or Genvoya® or unbranded elvitegravir/cobicistat/emtricitabine/tenofovir alafenamide PEP in a high risk population of HIV-1 seronegative adults
- Early cessation of regimen
- Frequency of adverse events
- Change from baseline in quality of life
- HIV-1 seroconversion
- Change from baseline in serum creatinine and eGFR
- Markers of proximal tubulopathy (glycosuria, proteinuria > 1+)
- Self-reported adherence
- Reasons for non-adherence

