Eligible HIV-negatives who accept participation in CRUSH, but who choose not to receive PrEP or are deemed ineligible to do so, will receive the same routine sexual health services described above. In addition to accessing as-needed services, they will be asked to schedule regular visits for study evaluations and interviews at 1, 6, and 12 months following enrollment. At each clinical visit, whether as-needed or scheduled, CRUSH participants will undergo NAT testing for detection of early HIV infection. They will also be offered participation in peer support groups, and may be asked to serve as “seeds” for social network recruitment. CRUSH clinicians will provide routine sexual health care as well as other basic and urgent medical care. Participants with other complex medical problems will be assisted by CRUSH staff in securing appropriate referrals for ongoing clinical care.

HIV-negative participants with any of the following **will not be offered PrEP**:

- History of pathological bone fractures not related to trauma;
- Renal disease or known abnormal serum creatinine;
- Urine dipstick with persistent proteinuria $\geq 2+$;

- Concomitant participation in a clinical trial using investigational agents, including placebo-controlled clinical trials using such agents; or
- Any other condition that would preclude provision of informed consent; make participation in the project unsafe; complicate interpretation of outcome data; or otherwise interfere with achieving the project objectives, based on the opinion of the investigators and/or treating clinician.
- Women who are currently breastfeeding.

VII.6 HIV Negative CRUSH Participants who opt in to PrEP

Participants who have a negative HIV1/2 antibody point of care result will receive sexual health promotion counseling at the time they are provided their results. Participants will be asked if they would like to receive PrEP as part of their participation in the study. CRUSH participants who choose not to receive PrEP at screening for CRUSH may choose to initiate PrEP at a later visit, if still eligible.

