PEP should be started as soon as possible, and before the results of RNA testing are known, and in all cases within 72 hours of the last possible exposure to HIV. If the HIV RNA test result is negative, viral symptoms resolve, and repeat rapid antibody testing is non-reactive, PEP should be discontinued and the participant may at that point be offered PrEP. If the HIV RNA test result is positive, the participant will be immediately referred to the TLC+ arm of CRUSH. Some participants with no high risk exposures in the 72 hour PEP window, but at ongoing high risk and with symptoms and/or signs highly suggestive of acute HIV infection, may elect to start presumptive highly antiretroviral therapy (HAART); these participants will be referred immediately to an expert HIV clinician.

Creatinine testing will also be performed on the screening blood sample for participants intending to receive PrEP, and a urine dipstick will be performed to assess for proteinuria. Dipstick proteinuria of 2+ or greater will exclude the participant from receiving PrEP; these participants will be referred for clinical evaluation. If the urine dipstick is 1+, PrEP will be deferred and the participant will be asked to return in one week for a repeat dipstick. If a participant's enrollment creatinine is normal and repeat dipstick remains <2+, s/he may begin PrEP.

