Symptoms and laboratory parameters associated with potential toxicities of FTC/TDF will be monitored as described above. As is true for all patients of EBAC/DYC, study participants will have received instructions for contacting the clinic to report any adverse signs or symptoms that they experience. Grade 3 or 4 adverse events, as defined by the DAIDS Table for Grading the Severity of Adult and Pediatric AEs, Version 1.0, December, 2004 (Clarification August 2009) will be recorded on the Adverse Event form. All Adverse Events will be evaluated by an EBAC/DYC clinician. Symptomatic Grade 3 events and Grade 4 adverse events will be reported to CHRP and Gilead Sciences by the investigators regardless of relation to the study drug.

IX. 1.1 Creatinine elevation

For an estimated glomerular filtration rate (eGFR) less than 60 ml/min/1.73m², serum creatinine will be repeated as soon as possible within 7 days. If the eGFR remains less than 60, FTC/TDF will be held until the eGFR is again greater than 60, at which point the participant may be re-challenged with FTC/TDF after consultation with the Principal Investigator ([name]). If the eGFR again falls below 60 after the drug is restarted, FTC/TDF will be permanently discontinued, and the participant will be monitored until the eGFR returns to baseline or stabilizes.

IX. 2 Urine protein detection

Any participant with protein of 1+ or greater on urine dipstick analysis will have the urine dipstick repeated within a week. If the creatinine is normal and the repeat dipstick is < 2+ the participant may remain on PrEP. Participants who have dipstick of $\geq 2+$ will have PrEP discontinued and will be referred to a nephrologist. If the nephrologist does not recommend against restarting PrEP, the participant can restart. Participants with evidence of renal toxicity attributable to FTC/TDF will have the study drug stopped

IX. 3 HIV acquisition /suspected acute HIV infection

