Appendix 4:

Study Visit Schedule

Study Visit Schedule (

Week	Screening*	0	4	12, 24, 36, 48		Stop drug	HIV Ab+
Clinical Assessments/Interventions							
Screen inclusion/exclusion criteria	x						
Obtain informed consent	x						
Medical history and focused review of systems	x	x	x	x		x	x
STI Risk Assessment	x	x	x	x		x	x
Adherence Assessment			x	x		x	x
Targeted Physical Exam	x	x	x	x		x	x
Adherence counseling		x	x	x		x	x
Risk reduction counseling, condom distribution	x	x	x	x		x	x
Drug dispensing		x	x	x			
ACASI (weeks 0, 4, 24, 48 only)		x	x	x			
Laboratory Assessments							
Creatinine	x		x	x			
Urine dipstick protein	x	x	x	x			
Rapid urine pregnancy test (if relevant)	x	x	x	x		x	x
HBsAg (and HBsAb if not documented)	x						
ALT/AST (if HBsAg+)		x	x	x		x	x
HBV DNA + LFTs(if HBsAg+)		x	x	x		x	x
Serum HIV Ab EIA	x					x	
Rapid Oral HIV Ab	x	x	x	x		x	
HIV Ab Western Blot							x
HIV RNA Qualitative PCR	x						
HIV RNA Qualitative PCR (risk-guided)			x	x		x	
HIV RNA Quantitative PCR							x
HIV-1 genotype							x
STI laboratory evaluation	x			x		x	x
DBS Drug Level Testing			x	x		x	x
*-4 to -1 weeks September 2013						Page 40 of 53	

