## Statistical Analysis Plan

Descriptive statistics (frequencies, means, medians) will be used to characterize endpoint variables. Univariate tests of association (T test, Chi square) will be used to test for association between demographic variables and key endpoints such as adherence, early cessation of regimen, and frequency of adverse events, as well as between assigned PEP regimen and these endpoints. Changes in quality of life will be tested for association with early regimen cessation and with assigned PEP regimen. Changes in serum creatinine will be summarized with descriptive statistics (mean, standard deviation) and compared to historical data from clinical trials.

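### Urine glucose is not specified anywhere in the protocol, and no end-of-course renal test is scheduled for PEP, so the SAP's PEP renal endpoints cannot be reported as listed

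*SAP*

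**What the plan says.** The SAP's list of secondary endpoints begins with an objective "To assess the renal safety of Stribild® or Genvoya" (or an unbranded equivalent) given as PEP. It goes on to name change from baseline in serum creatinine and eGFR, and then "Markers of proximal tubulopathy (glycosuria, proteinuria > 1", with the cut-off printed as above 1+. For analysis, the SAP describes all endpoint variables with frequencies, means and medians. The only renal measure it treats specifically is creatinine: "Changes in serum creatinine will be summarized with descriptive statistics (mean, standard deviation" and compared with historical trial data. It gives no rule for combining the two urine markers, for handling a missing reading, or for separating new findings from those present at baseline.

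The protocol's renal urine testing is as follows.

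- Section VII.5, reasons for not offering PrEP: "Urine dipstick with persistent proteinuria" of 2+ or more.
- Section VII.6, screening: "Creatinine testing will also be performed on the screening blood sample for participants intending to receive PrEP", and in the same sentence "a urine dipstick will be performed to assess for proteinuria".
- Section IX.2, on treatment: "Any participant with protein of 1+ or greater on urine dipstick analysis will have the urine dipstick repeated within a week".
- Appendix 4, visit schedule: a row labelled "Urine dipstick protein".

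PEP appears in section VII.6 as a 28-day, three-drug course offered after a recent high-risk exposure. nPEP is also listed as a clinical procedure in section IV. Appendix 4 has no PEP column.

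**The concern.** An endpoint needs a specified measurement, time point and record. The SAP asks for two urine markers and the protocol specifies one. The SAP also asks for renal change over PEP, whereas the protocol's renal schedule is built around PrEP visits. If both documents are followed to the letter, the analyst reaches database lock with no glycosuria field and no planned post-course creatinine or dipstick for PEP recipients. The risk is that a renal-safety statement then rests on dipstick protein alone, from a pathway other than the one the SAP names, without the report making that clear. Because the planned analysis is descriptive, no later modelling step would recover a reading that was not recorded.

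**Working it through.** There is no sample-size, power or event figure to reproduce. The check sets each urine and creatinine test in the protocol against the SAP endpoint.

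**1. Analyte.** The four places above (VII.5, VII.6, IX.2, Appendix 4) name protein and nothing else. Glycosuria and urine glucose do not occur in the supplied protocol text. The protocol's other named urine test is the rapid pregnancy test, which has no renal purpose.

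**2. Time points in Appendix 4.**

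- Urine protein: screening (1) + week 0 (1) + week 4 (1) + weeks 12, 24, 36, 48 (4) = 7.
- Urine glucose: 0 of those 7.
- Creatinine: screening (1) + week 4 (1) + weeks 12, 24, 36, 48 (4) = 6; week 0 is not marked.
- The column for stopping drug is marked for neither dipstick nor creatinine, so it cannot stand in for an end-of-PEP test.

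**3. Population.** Section VII.6 ties the screening creatinine and dipstick to people intending to take PrEP. PEP is offered within that same assessment, so a person diverted to PEP there may have a baseline creatinine and protein dipstick. Nothing comparable is specified for nPEP users who arrive by another route. For neither group is a creatinine or dipstick scheduled at the end of the course. Someone who later moves from PEP to PrEP would meet the PrEP dipsticks, but these are not timed to the PEP course, and such people are a selected subset.

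**4. Result by marker.**

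| SAP item | PrEP pathway | PEP recipients |
|---|---|---|
| Proteinuria above 1+ | 7 scheduled readings | possible baseline; no end-of-course reading |
| Glycosuria | none specified | none specified |
| Change in creatinine and eGFR | 6 scheduled creatinines | possible baseline; no end-of-course value |

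**5. Protein threshold.** On a graded strip, above 1+ is the same as 2+ or more, so the SAP cut-off and the protocol's 2+ cut-off agree.

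**The case against.** The strongest reply is that this is one symptom of a wider mismatch. The SAP speaks of assigned PEP regimens, quality of life and elvitegravir-based products. The protocol is a Truvada PrEP and sexual-health demonstration project that never names those products. Setting a PEP endpoint against a PrEP schedule may compare two different plans. That stands, and it limits the claim: one cannot say that the glucose gap would survive every possible realignment. A rewritten SAP might drop glycosuria, and a PEP schedule might include glucose. As the two documents now read, however, the endpoint has no source, and aligning drug names alone would not add a glucose field.

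Several stronger readings are tempting, and the documents do not support them.

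- *Glucose is never measured.* The type of strip is not stated and it may carry a glucose pad. What can be said is that glucose is not specified or recorded.
- *Renal safety will look better than it is.* This assumes that an unmeasured glucose is scored as negative. The SAP lists markers and defines no composite, so glycosuria could equally be reported as not available. The bias is a possibility that a clear rule would remove.
- *PEP recipients have no renal baseline.* Those reached through PrEP screening may have one; the gap is at the end of the course and for other routes into PEP.
- *Creatinine can be run on the NAT blood.* Appendix 12 sends that sample under a de-identified code to an outside laboratory, so creatinine needs its own specimen.

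Some parts of the documents were not available and several appendices appear by title only, so the finding is confined to the supplied text.

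**Conclusion.** The concern holds in limited form. Urine glucose is specified at 0 of 7 scheduled dipsticks, and no end-of-course creatinine or dipstick is scheduled for PEP, so the glycosuria marker and the PEP renal-change endpoints cannot be reported as listed. A reader might turn the count of one marker out of two into a 50% loss, or into zero sensitivity for glycosuria-only cases. Neither describes the effect on the conclusion: the documents give no frequency of glycosuria and no number of PEP recipients, so neither the size nor the certainty of a bias can be stated. The finding assumes that the SAP and protocol are meant to be used together and that no unavailable form or appendix records urine glucose or sets a PEP laboratory schedule. It concerns secondary safety endpoints and does not affect the project's three main aims. It should be corrected because a named endpoint otherwise has no planned data.

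**What to change.** 1. Change the Appendix 4 row to *Urine dipstick: protein and glucose*, and record both readings at every scheduled dipstick, including baseline. Confirm that the strip in use has a glucose pad. In the SAP, state the positivity threshold for glucose, report each marker separately with its number measured, and treat an unmeasured glucose as missing, not negative. If this is not wanted, delete glycosuria from the SAP.

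2. Reconcile the SAP's PEP renal endpoints with the protocol's visit schedule. Either state the analysis population and the baseline and post-course time points at which PEP recipients' creatinine and dipstick data are collected, with creatinine on its own specimen, or remove those endpoints. Which tests and timings are clinically appropriate is for the investigators to settle.

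The first change costs one extra field per dipstick. Appendix 1 projects 135 participants interested in PrEP. If all took it and completed week 48, that is at most 135 × 7 = 945 additional scheduled readings, from strips already being used if they carry a glucose pad. The second costs a small amount of laboratory work if the PEP endpoints are kept, and only document wording if they are removed.

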member will provide risk reduction counseling, provide the participant with condoms, and schedule a follow up visit for 4 weeks. When all study activities for the day are complete and documented on a dispensing checklist, the pharmacy will dispense one bottle (30 pills) of Truvada® to the participant.

Participants found to be hepatitis B antigen positive, who choose not to take PrEP, will be referred to either their primary care provider or another community based clinic for treatment of hepatitis B infection. Participants who are HBsAg-positive and who initiate PrEP will be informed that stopping PrEP could cause a hepatitis flare and/or hepatitis B drug resistance. The clinical stage of their liver disease will be assessed at PrEP initiation (see Appendix Q), including testing for AST/ALT, total bilirubin, alkaline phosphatase, prothrombin time, and albumin, and a clinical evaluation for stigmata of cirrhosis. Participants who are HBsAg positive and who receive PrEP will have their hepatitis B DNA viral load and their AST/ALT monitored for the duration of their PrEP use and for 6 months following discontinuation of PrEP.

VII.8 One Month Visit

At the 1-month visit, participants will have a rapid HIV antibody test, sexual health promotion counseling, and PrEP-specific counseling. Participants will meet with the study clinician for a medical history and targeted physical exam. For participants who are still interested in receiving PrEP, a blood sample will be drawn for creatinine and for dried blood spot (DBS) testing of drug levels. Additionally for those participants who are HBsAg positive, blood will be drawn for ALT/AST and hepatitis B DNA. Participants who remain eligible to receive PrEP will be provided two bottles (60 pills) at this visit. Women of reproductive potential will have a rapid urine pregnancy test.

VII.9 Subsequent visits

Subsequent visits will occur according to the schedule shown in the table of Study Procedures. Following the 1 month follow up visit, participants will be asked to return to the clinic in 2 more months (at 3 months of participation), and then every 3 months thereafter for study visits (i.e., at months 3, 6, 9

and 12). These visits will be scheduled within +/- 2 weeks of the target date based on PrEP initiation. Participants who elect to continue PrEP beyond 48 weeks will continue to be assessed every 3 months for the duration of the project period, or until they cease PrEP.

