At quarterly visits, participants will receive rapid HIV testing and counseling, and will meet with a clinician for a medical history. If they report a possible STI exposure or have symptoms of an STI, they will be tested and treated as appropriate. Participants will also receive PrEP-specific counseling, be asked to provide a blood sample for creatinine and for dried blood spot (DBS) drug level testing, and be dispensed 3 bottles (90 pills) of PrEP. Women of reproductive potential will have a rapid urine pregnancy test at all scheduled visits. At semiannual visits, in addition to the quarterly procedures, participants will have STI and serum HIV antibody testing done, a targeted physical exam will be performed, and they will be asked to complete an ACASI questionnaire. Participants who are HBsAg positive will have ALT/AST and HBV DNA viral load testing done.

VIII. Assessments and Interventions

Assessments and interventions taking place at each visit are described below.

VIII.1 Risk assessment and clinician counseling

Risk assessments will be conducted using "Five P's," a simple approach to risk assessments for clinicians recommended by the California STD Prevention Branch (CA STD Branch, 2011).⁸ The five P's stand for Partners, sexual Practices, Past STIs, Pregnancy history and plans (if relevant), and Protection from STIs. Sexual risk information will be entered into the clinical notes. The clinician will document performance of a risk assessment on the Dispensing Checklist, and perform brief counseling regarding risk reduction.

VIII.2 Pregnancy and breastfeeding assessment and counseling

Female participants of reproductive potential (anatomically female, premenopausal, with an intact uterus) will be screened at each visit for pregnancy, plans to become pregnant, and current breastfeeding.

All women who are pregnant at enrollment or become pregnant during their participation will be immediately linked to prenatal care. The clinician will:

- a. Determine if women are planning to become pregnant, are currently pregnant, or are breastfeeding;
- b. Disclose to women that safety for infants exposed to Truvada® during pregnancy has not been fully assessed but that no harm has been reported;
- c. Do not offer (or, if already begun, cease) PrEP to women who are breastfeeding;
- d. Conduct a pregnancy test and document results; if pregnant, discuss continued use of PrEP with patient and prenatal care provider;

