- e. Before dispensing PrEP, ensure that a urine pregnancy test is negative or, if pregnant, that the patient has been informed about Truvada® use during pregnancy; and
- f. Upon discontinuation of PrEP in a pregnant participant, inform prenatal care provider of TDF/FTC use in early pregnancy and coordinate care to maintain HIV prevention during pregnancy and breastfeeding.

VIII.3 Adherence assessment and counseling

Adherence counseling (motivational counseling) will be performed at every visit while participants are receiving PrEP, as part of an Integrated Next-Step Counseling approach⁹. This client-centered approach will not be assessment-based. The counseling conversation will focus on facilitators and barriers to pill-taking, and strategies for making pill-taking more manageable for the participant. In the second portion of the visit with the study coordinator or other DYC staff member, a pill count will be conducted. Pill counts will be compared to the expected number of pills remaining, and the study coordinator will inform the participant of the degree of discrepancy. If drug levels are available from the prior visit's dried blood spot (DBS) testing, results will be shared with the participant and discussed. Adherence counseling following the model above will be repeated.

Adherence will be further assessed on the semiannual ACASI questionnaire. Additionally, at the time of each DBS collection, participants receiving PrEP will be asked about the timing of their most recent three Truvada® doses, in order to aid in interpretation of DBS results. An assessment tool used in conjunction with integrated next step counseling is included in appendix 10.

VIII.4 Medical history and focused review of systems

Symptoms of STIs including acute HIV infection will be assessed and recorded in the clinical notes according to usual clinic practice. The medical history will also ask about potential side effects of Truvada®. The clinician will verify that there are no symptoms of acute HIV on the Dispensing Checklist.

VIII.5 Targeted physical exam

The clinician will perform a targeted exam as required based upon the medical history and focused review of systems and record the results in the clinical notes.

VIII.6 Risk Reduction/Sexual health promotion counseling

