Sexual health promotion counseling will be performed at every scheduled visit for all participants. The counseling approach will follow the Integrated Next-Step Counseling model. The counseling conversation will review which sexual health promotion strategies the participant uses, their facilitators and barriers to their use, and an agreement on which strategies the participant would like to continue or try to use.

VIII.7 Laboratory evaluation

The clinician will order appropriate laboratory studies at the conclusion of the visit, and check off which labs were ordered on the Dispensing Checklist. Prior to dispensing, the study coordinator or DYC staff member will verify that all required lab specimens were submitted to the on-site clinical lab.

VIII.8 Drug level assay: Dried Blood Spot Testing

Blood will be drawn, processed, stored, and shipped for dried blood spot (DBS) testing of intracellular levels of tenofovir and emtricitabine, at timepoints as shown in the schedule of visits. Drug

level data may become available before the participant's next scheduled study visit. If these data demonstrate likely inadequate adherence, the participant will be contacted and brought in for an additional visit, which will focus on adherence support using the Integrated Next-Step Counseling model.

VIII.9 STI evaluation and treatment

Sexually transmitted infections will be evaluated and treated in accordance with usual clinic procedures, which are consistent with CDC guidelines and include screening for asymptomatic infections among high risk groups (inclusive of all study participants), evidence-based treatment, expedited partner therapy, and prompt public health reporting.

VIII.10 Pharmaceutical dispensing

At PrEP initiation a staff member will provide the pharmacy the prescription for PrEP initiation and hand the bottle to the participant at the visit. At subsequent, scheduled visits the clinician may fill a prescription prior to the visit and dispense it to the participant directly after eligibility has been confirmed.

VIII.11 Participant retention

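### The available SAP text measures adherence only by self-report and only for PEP, so the drug levels and pill counts collected on PrEP have no planned analysis

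*SAP*

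**What the plan says.** **SAP.** The Statistical Analysis Plan section treats adherence as a key endpoint. It is to be tested by t test or chi-square against demographic variables, "as well as between assigned PEP regimen and these endpoints". That section gives no measure, threshold or time point. The Secondary Endpoints list names one measure, "Self-reported adherence". The related objective begins "To assess adherence to Stribild® or Genvoya" and concerns those products given as PEP. Neither section mentions drug levels or pill counts.

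**Protocol, drug levels.** Section VIII.8 states: "Blood will be drawn, processed, stored, and shipped for dried blood spot (DBS) testing of intracellular levels of tenofovir and emtricitabine". At the one-month visit (VII.8), for those still interested in PrEP, "a blood sample will be drawn for creatinine and for dried blood spot (DBS) testing of drug levels". At quarterly visits (VII.9) participants will "be asked to provide a blood sample for creatinine and for dried blood spot (DBS) drug level testing". Appendix 4 marks DBS at weeks 4, 12, 24, 36 and 48, at the stop-drug visit and at the HIV-antibody-positive visit.

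**Protocol, other adherence measures.** Section VIII.3 places a pill count within on-PrEP adherence counselling: "Pill counts will be compared to the expected number of pills remaining". It also says: "Adherence will be further assessed on the semiannual ACASI questionnaire". At each DBS collection, participants on PrEP are asked when they took their last three doses, to help interpret the level.

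**The concern.** The protocol collects an objective measure of PrEP exposure on a regular schedule, but the available SAP text gives it no endpoint, no categories and no test. PrEP sits within Aim 3, which the protocol places at the centre of the project, so how well participants take it is a question the study will be expected to answer.

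Two things could go wrong. First, PrEP adherence might be reported from ACASI because self-report is the only measure the SAP names. Under section VIII.3, staff tell participants their pill-count discrepancy and any available earlier drug level. Later ACASI answers therefore come from people who have had that feedback, and over-reporting is a realistic risk. If over-reporting is equal across groups, it dilutes the demographic comparisons the SAP plans. If it is unequal, it can create or hide differences. Second, the DBS data might be analysed anyway, with cut-offs chosen after the results are known.

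**Working it through.** The documents state no power, alpha or target figure for adherence, so there is no plan figure to reproduce. The check has three parts.

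**1. Which measure belongs to which regimen**

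| Measure | Regimen | Source | Visible planned analysis |
|---|---|---|---|
| Self-report | Stribild/Genvoya-type PEP | SAP, Secondary Endpoints | Adherence tested against demographics and PEP regimen |
| DBS levels | Truvada PrEP | Protocol IV, VII.8, VII.9, VIII.8, Appendix 4 | None |
| Pill count | Truvada PrEP | Protocol VIII.3 | None |
| ACASI adherence items | On-PrEP adherence, as VIII.3 describes them | Protocol VIII.3 | None specific to PrEP |
| Last-three-dose recall | Truvada PrEP | Protocol VIII.3 | None; collected to interpret DBS |

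For PEP, section VII.6 describes a 28-day three-drug course with no DBS and no pill count.

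**2. Scheduled measurements after PrEP initiation, weeks 4 to 48**

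- DBS: weeks 4, 12, 24, 36, 48 = 5. There is none at week 0, the initiation visit.
- ACASI: weeks 4, 24, 48 = 3 (Appendix 4), or weeks 24 and 48 = 2 if the adherence items are strictly semiannual (VIII.3).
- ACASI coverage of the DBS time points: 3/5 = 60%, or 2/5 = 40%.
- Three-dose recall: 5/5, because it accompanies each DBS.
- ACASI is not scheduled at the stop-drug visit; DBS is.

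Appendix 1 projects 450 × 30% = 135 HIV-negative participants interested in PrEP. If all started and stayed on it, the schedule would yield 135 × 5 = 675 DBS values, against 135 × 3 = 405 or 135 × 2 = 270 ACASI reports. These are ceilings, since PrEP is optional and can be stopped.

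**3. Effect of over-reporting on a group comparison**

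Treat adherence as binary, with true proportion p and self-report sensitivity Se and specificity Sp equal in both groups. The observed proportion is p × Se + (1 − p) × (1 − Sp), so

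observed gap = true gap × (Se + Sp − 1).

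All inputs here are assumptions: true adherence 50% and 70%, Se = 95%, and Sp varied because the documents give no value.

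| Sp | Se + Sp − 1 | Group truly 50% | Group truly 70% | Observed gap (true 20) |
|---|---|---|---|---|
| 50% | 0.45 | 0.475 + 0.250 = 72.5% | 0.665 + 0.150 = 81.5% | 9 points |
| 70% | 0.65 | 0.475 + 0.150 = 62.5% | 0.665 + 0.090 = 75.5% | 13 points |
| 90% | 0.85 | 0.475 + 0.050 = 52.5% | 0.665 + 0.030 = 69.5% | 17 points |

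The gap shrinks in every row. Adherence is overstated in both groups at 50% and 70% specificity. At 90% the levels are close to the truth, and the higher group is slightly understated.

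**The case against.** The strongest objection is that the SAP endpoint and the protocol's objective data concern different regimens. A reader might infer that the SAP's adherence endpoint rests on a weak measure while better data for it lie unused. The documents do not support that. The endpoint is PEP adherence, and neither drug levels nor pill counts are described for PEP. This objection stands in full. What remains is that PrEP adherence has no planned analysis in the available text.

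A reader might also infer that self-report as a whole is sparser than DBS, or absent when drug is stopped. That is true of ACASI only. Three-dose recall is taken with every DBS, including at the stop-drug visit, where Appendix 4 also marks an adherence assessment. The recall is, however, described as an aid to reading the DBS result and not as an adherence outcome.

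The size of the bias is uncertain. ACASI is completed privately and identified only by study number (VI.2), which should limit desirability bias. Pill counts can also be influenced by the feedback given on them. These points stand, which is why specificity is shown as a range and pill count is proposed only as support.

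Nor are the objective data wholly unused: sections VIII.3 and VIII.8 use them for participant feedback and extra adherence visits. The gap lies in the statistical analysis. Finally, part of the SAP was not available for this review, and a PrEP adherence definition there cannot be ruled out.

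**Conclusion.** The point holds in this limited form: the available SAP text has no PrEP adherence endpoint, so DBS levels scheduled at five on-PrEP follow-up visits, and the pill counts, have no prespecified statistical use.

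Relying on ACASI instead would leave 40% to 60% of the DBS time points covered. Under the stated assumptions, it would show a true 20-point difference as 9 to 17 points. That range rests on a binary definition, 95% sensitivity, specificity of 50% to 90% and equal misclassification in both groups. None of these comes from the documents, and the SAP's mention of t tests leaves open a continuous measure, to which the formula does not apply. The mismatch between the regimens and the measurement counts does not depend on these assumptions.

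It would go too far to say that the whole remedy uses data already collected. That is so for PrEP; an objective measure for PEP would need collection that the protocol does not describe. This is a change the sponsor should make, with moderate confidence given the unavailable SAP text.

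**What to change.** 1. Add a PrEP adherence endpoint to the SAP, based on DBS level categories fixed before analysis, at weeks 4, 12, 24, 36 and 48. State the denominator at each time point (participants still on PrEP) and how missing samples are handled.
2. Test that endpoint against demographic variables, as the SAP already intends for adherence.
3. Report pill count and self-report as supportive measures, each with its agreement with DBS.
4. State that self-report is the measure for the PEP endpoint, for which the documents describe no drug levels or pill counts.
5. Reconcile the PEP regimens in the SAP with the PrEP programme in the protocol, so that each adherence endpoint names its regimen and population.

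Counting missed visits as non-adherent is not recommended. It would mix stopping PrEP with taking it poorly, and early cessation is already a separate SAP endpoint.

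For PrEP the cost is SAP wording, since sample collection is already scheduled. The downside is that the reported adherence figure will probably be less favourable than one from self-report.
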